#### 7.5 SECONDARY ENDPOINT

#### 7.5.1 Key secondary endpoint

This section is not applicable as no key secondary endpoint has been specified in the protocol.

#### 7.5.2 (Other) Secondary endpoint

#### 7.5.2.1 Primary analysis of the secondary endpoint

The MCPMod approach will be applied to the secondary endpoint of change from baseline in SCoRS total score by interviewer at Week 12 using an ANCOVA model including treatment and baseline SCoRS total score as covariates using the FAS.

### Boehringer Ingelheim TSAP for BI Trial No: 1346.9

Proprietary confidential information © 2020 Boehringer Ingelheim International GmbH or one or more of its affiliated companies

Page 28 of 34

#### 7.7 EXTENT OF EXPOSURE

Extent of exposure will be summarised for the treated set using descriptive statistics for days of exposure as well as number (%) of subjects whose total exposure falls in the defined categories: <30 days, 30 to <42 days, 42 to <60 days, 60 to <90 days, >=90 days.

#### 7.8 SAFETY ANALYSIS

All safety analyses will be performed on the treated set and other subject sets as appropriate.

#### 7.8.1 Adverse Events

Unless otherwise specified, the analyses of AEs will be descriptive in nature. All analyses of AEs will be based on the number of subjects with AEs and not on the number of AEs. The reporting and analyses of AEs will follow the BI guideline ( $\underline{8}$ ). AEs will be coded with the most current version of MedDRA®.

For analysis multiple AE occurrence data on the CRF will be collapsed into an AE provided that all of the following applies:

- All AE attributes are identical (lower level term (LLT), intensity, action taken, therapy required, seriousness, reason for seriousness, relationship, outcome)
- The occurrences were time-overlapping or time-adjacent (time-adjacency of 2 occurrences is given if the second occurrence started on the same day or on the day after the end of the first occurrence).

For further details on summarisation of AE data, please refer to (4, 8).

The analysis of AEs will be based on the concept of treatment emergent adverse events. That means that all adverse events occurring between the date of the first administration of trial treatment till the date of the last administration of trial treatment + residual effect period will be assigned to the on-treatment period label with the trial treatment assigned on Day 1 of the first treatment cycle. All AEs occurring before the first administration of trial treatment will be assigned to 'screening' and all AEs occurring after the residual effect period will be assigned to 'follow-up'. For details on the treatment definition, see Section 6.1.

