5.3.7 Adverse event collection and reporting

AE Collection

The following must be collected and documented on the appropriate CRF(s) / eCRF by the Investigator:

From signing the informed consent onwards through the Residual Effect Period (REP) until the individual patient's end of trial:

all AEs (serious and non-serious) and all AESIs.

Figure 5.3.7: 1 Collection and reporting of AEs/SAEs during the study

The REP is defined as 11 days after the last trial medication application. All AEs which occurred through the treatment phase and throughout the REP will be considered as on treatment (please also see Section 7.3.4). Events which occurred after the REP will be considered as post treatment events.

AE reporting to sponsor and timelines

The Investigator must report SAEs, AESIs, and non-serious AEs which are relevant for the reported SAE or AESI, on the BI SAE form via fax immediately (within 24 hours) to the Sponsor's unique entry point (country specific contact details will be provided in the ISF). The same timeline applies if follow-up information becomes available. In specific occasions the Investigator could inform the Sponsor upfront via telephone. This does not replace the requirement to complete and fax the BI SAE form.

Before administration of study medication at Visit 2, site staff will remind patients to report "any unusual visual perception they may experience". If patients report a change in perception or any vision-related AE, site staff must record the patient's verbatim description in the source documents and report it in the same way in the CRF (and SAE form, if applicable). A local ophthalmology assessment will be required if any visual AE is rated as moderate or severe by the subject or at the discretion of the PI. The ophthalmologist will act as a consultant to the Investigator and may offer advice on the proper management and treatment for the reaction.

In case of anemia with unknown reason as measured by the central laboratory the investigator should consult with an internist. Any clinically relevant finding from the internist's consultation should be reported as an AE.

For Japan: All SAEs and AESIs must be reported immediately to the head of the trial site.

With receipt of any further information to these events, a follow-up SAE form has to be provided. For follow-up information the same rules and timeline apply as for initial information.

Information required

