For each AE, the Investigator should provide the information requested on the appropriate (e)CRF pages and the BI SAE form, e.g. onset, end date, intensity, treatment required, outcome, seriousness, and action taken with the investigational drug(s). The Investigator should determine the causal relationship to the trial medication and the trial procedures outlined under Section 6.2.

The following should also be recorded as an (S)AE in the (e)CRF and SAE form (if applicable):

- Worsening of the underlying disease or of other pre-existing conditions
- Changes in vital signs, ECG, physical examination and laboratory test results, if they are judged clinically relevant by the Investigator.

If such abnormalities already pre-exist prior trial inclusion they will be considered as baseline conditions.

All (S)AEs, including those persisting after individual patient's end of trial must be followed up until they have resolved, have been sufficiently characterized, or no further information can be obtained.

Pregnancy

In the rare case that a female subject participating in this clinical trial becomes pregnant after having taken trial medication, the Investigator must report immediately (within 24 hours) the drug exposure during pregnancy (DEDP) to the Sponsor's unique entry point (country-specific contact details will be provided in the ISF). The Pregnancy Monitoring Form for Clinical Trials (Part A) should be used.

The outcome of the pregnancy associated with the drug exposure during pregnancy must be followed up and reported to the Sponsor's unique entry point on the Pregnancy Monitoring Form for Clinical Trials (Part B).

As pregnancy itself is not to be reported as an AE, in the absence of an accompanying SAE, only the Pregnancy Monitoring Form for Clinical Trials and not the SAE form is to be completed. If there is an SAE associated with the pregnancy then the SAE has to be reported on the SAE form in addition.

The ISF will contain the Pregnancy Monitoring Form for Clinical Trials (Part A and B).

Page 57 of 116

Proprietary confidential information © 2019 Boehringer Ingelheim International GmbH or one or more of its affiliated companies

Page 58 of 116

Proprietary confidential information © 2019 Boehringer Ingelheim International GmbH or one or more of its affiliated companies

Page 59 of 116

Proprietary confidential information © 2019 Boehringer Ingelheim International GmbH or one or more of its affiliated companies

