7.3.4 Safety analyses

Adverse events will be coded using the Medical Dictionary for Regulatory Activities (MedDRA) coding dictionary. Standard BI summary tables and listings will be produced. All adverse events with an onset between the start of treatment and the end of the residual effect period (REP), a period of 11 days after the last dose of trial medication, will be assigned to the treatment period for evaluation.

All treated patients will be included in the safety analysis and will be summarized under the actual trial medication received at randomization. In general, safety analyses will be descriptive in nature and will be based on BI standards. No hypothesis testing is planned.

Statistical analysis and reporting of adverse events will concentrate on treatment-emergent adverse events. To this end, all adverse events occurring between the start of treatment and the end of the residual effect period will be considered 'treatment-emergent'. The residual effect period is defined as 11 days after the last dose of trial medication. Adverse events that start before first drug intake and deteriorate under treatment will also be considered as 'treatment-emergent'.

Frequency, severity, and causal relationship of adverse events will be tabulated by system organ class and preferred term after coding according to the current version of the MedDRA. Frequency tables for all adverse events, protocol-specified adverse event of special interest (AESI), serious adverse event (SAE), adverse event leading to death, adverse event leading to discontinuation, investigator assessed drug-related adverse event and serious adverse event will be generated for treatment-emergent adverse events. In addition, summary statistics and descriptive analyses will be conducted for other safety parameters including worsening of disease state as assessed by PANSS and suicidality as assessed by C-SSRS.

Laboratory data will be analysed both quantitatively as well as qualitatively. The latter will be done via comparison of laboratory data to their reference ranges. Values outside the reference range as well as values defined as clinically relevant will be highlighted in the listings. Treatment groups will be compared descriptively with regard to distribution parameters as well as with regard to frequency and percentage of patients with abnormal values or clinically relevant abnormal values.

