### 6. GENERAL ANALYSIS DEFINITIONS

#### 6.1 **TREATMENTS**

For basic trial information on treatments to be administered, assignment of dose group, and selection of doses, see CTP Section 4.

Long Name	Short Name
Placebo	Placebo
BI 425809 2 mg QD	BI 2mg
BI 425809 5 mg QD	BI 5mg
BI 425809 10 mg QD	BI 10mg
BI 425809 25 mg QD	BI 25mg

Table 6.1: 1Treatment descriptions

 Table 6.1: 2
 Analysing treatment periods (same for all treatment groups)

Analysing Treatment Period	Start Date	Stop Date
Screening	Date of informed consent	Date of the first treatment administration
On-treatment	Date of the first treatment administration	Date of the last treatment administration + REP + 1 day
Follow-up	Date of the last treatment administration + REP + 1 day	Date of the last per protocol visit

REP is the residual effect period which is defined as 11 days after the last dose of trial treatment.

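### SAP 7.8.1 drops, without declaring it, the protocol rule that AEs starting before first dose and worsening on treatment are treatment-emergent, so these events may be under-counted

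*SAP*

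**What the plan says.** **Protocol 7.3.4 (Safety analyses)** gives two routes to treatment-emergent status. The first is timing: an AE that occurs between the start of treatment and the end of the residual effect period. The second is worsening: "Adverse events that start before first drug intake and deteriorate under treatment will also be considered as 'treatment-emergent". On the length of the window it says: "The residual effect period is defined as 11 days after the last dose of trial medication".

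**SAP 7.8.1 (Adverse Events)** takes over the same concept: "The analysis of AEs will be based on the concept of treatment emergent adverse events". It then defines the concept by timing only. Events from first dose to last dose plus the residual effect period are on-treatment, and later events are follow-up. For earlier events: "All AEs occurring before the first administration of trial treatment will be assigned to 'screening". The worsening route does not appear. SAP 6.1 uses the same window as the protocol: "REP is the residual effect period which is defined as 11 days after the last dose of trial treatment".

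**SAP Section 3** says that the SAP rests on the analysis specified in protocol Section 7, which contains the worsening rule. **SAP Section 4** declares one change or clarification, on the wording of the SCoRS endpoint, and nothing on AEs.

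Two further provisions bear on the effect. Protocol 5.3.7 lists among the things to be recorded as an (S)AE: "Worsening of the underlying disease or of other pre-existing conditions". SAP 7.8.1 merges several occurrences into one AE only if they overlap or adjoin in time and "All AE attributes are identical (lower level term (LLT), intensity, action taken, therapy required, seriousness, reason for seriousness, relationship, outcome".

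**The concern.** The two documents classify the same event differently. Take an AE that starts after consent, is still present at first dose and becomes worse on treatment. Under the protocol it is treatment-emergent. Under the SAP text, a programmer who finds one record with a pre-dose start date puts it in screening.

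Such events can arise in any patient. AEs are collected "From signing the informed consent onwards through the Residual Effect Period (REP) until the individual patient's end of trial", and the flow chart puts the screening visit 7 to 28 days before first dose.

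At stake are the percentage of patients with (S)AEs, which protocol 5.1.2 names as a secondary endpoint, and the AE tables by treatment in SAP 7.8.1. Those tables include one for events in follow-up but none for events in screening, so a worsened event left in screening has no named table. An omission of this kind can only lower a count.

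**Working it through.** The documents state no figure on this point, so there is none to reproduce. The check compares the rules and then works out what one patient is worth in a table.

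**1. The rules by type of event**

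| Event | Protocol 7.3.4 | SAP 7.8.1 |
|---|---|---|
| Starts from first dose to last dose + 11 days | Treatment-emergent | On-treatment |
| Starts before first dose, does not worsen | Not treatment-emergent | Screening |
| Starts before first dose, worsens under treatment | Treatment-emergent | Screening |

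The documents disagree only in the last row. The residual effect period is 11 days in both and is not the source of the difference.

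**2. When the disagreement reaches a table**

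- *Worsening entered as a new occurrence with an on-treatment start date.* Its intensity or seriousness differs from the earlier occurrence, so the SAP merging rule leaves it separate. It falls in the on-treatment window and is counted. Nothing is lost.
- *Worsening entered by updating the existing record, with its pre-dose start date kept.* The SAP sentence sends the record to screening, and the event is lost from the treatment-emergent tables.

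Protocol 5.3.7 asks for onset, end date and intensity for each AE, but gives no rule for dating a change in intensity. The SAP merging rule acts on occurrences already entered separately and does not create them. Neither document settles which case applies to an AE that began in screening.

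**3. Size per patient**

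Inputs: 84 patients planned per active arm, 168 on placebo and 504 in total (protocol 7.7); tables count subjects, not events (SAP 7.8.1); preferred-term tables use cuts of >2% and >5% (SAP 7.8.1).

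Change in a row for one omitted patient = 1/n:

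- active arm: 1/84 = 1.19 percentage points
- placebo: 1/168 = 0.60 points
- all arms together: 1/504 = 0.20 points

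The SAP does not say whether the cuts apply per arm or overall. One patient can matter either way:

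- active arm, >2% cut: 2/84 = 2.38% becomes 1/84 = 1.19%
- active arm, >5% cut: 5/84 = 5.95% becomes 4/84 = 4.76%
- all arms, >2% cut: 11/504 = 2.18% becomes 10/504 = 1.98%

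**4. Bounds on the number of patients**

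The lower bound is zero, if worsening is always a new occurrence. For any row, the upper bound is the number of patients whose pre-dose AE worsened on treatment and who have no other on-treatment event in that row. The documents give neither the number of such AEs nor the proportion that worsen.

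**The case against.** The strongest reply is that data capture already covers these events. Worsening of a pre-existing condition is itself recorded as an AE, and the SAP does not merge occurrences that differ in intensity or seriousness. Complaints found at screening will often be baseline conditions, so their worsening becomes an AE with onset on treatment. The SAP also says *occurring*, not *with onset*; it adopts the treatment-emergent concept and rests on protocol Section 7; and it defers to a company guideline that is not among the documents and may deal with the matter. The analysis is descriptive, with no hypothesis test.

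Much of this stands. It narrows the gap to AEs that begin between consent and first dose and worsen without a new occurrence being entered. It does not remove the conflict. The SAP sentence covers all pre-dose AEs without exception, and a guideline that cannot be seen cannot be credited with restoring the rule. The protocol also states the worsening rule in addition to the timing rule, which would be unnecessary if re-entry always did the work.

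Three stronger readings are tempting, and the documents do not support them:

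- *The tables will under-count.* This follows only if worsening is not re-entered with an on-treatment date, which the documents leave open.
- *The error flatters the drug.* An omission can only lower counts, but it favours active treatment only if such worsening is more common there. The documents do not show this.
- *The number affected can be estimated.* Assuming that 5-10% of 504 patients have an AE ongoing at first dose and that 10-20% of these worsen gives 504 × 0.05 × 0.10 = 2.5 to 504 × 0.10 × 0.20 = 10.1 patients. Neither rate is in the documents. The product also assumes that no worsening is captured separately and that no patient has another on-treatment event in the same row.

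**Conclusion.** The SAP rule is wrong as written: it contradicts the protocol's definition of a treatment-emergent AE, and SAP Section 4 does not declare the change. That conclusion rests on the two texts alone.

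An under-count is possible but not demonstrated. It depends on how sites enter worsening of an AE that began in screening, which neither document states. The number of patients could be zero. Where one is lost, the row falls by 1.2 points in an active arm or 0.6 points in placebo at the planned arm sizes, enough to move a preferred term across a tabulation cut. The change should be made because it is nearly free and removes a possible one-directional error from a secondary safety endpoint.

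**What to change.** In SAP 7.8.1:

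1. Carry over the protocol rule. A pre-dose AE that deteriorates between first dose and the end of the 11-day residual effect period is assigned to the on-treatment period.
2. Keep the screening label only for pre-dose AEs that do not deteriorate.
3. State how deterioration is identified and dated from the eCRF occurrence data. The protocol does not define it further, so the SAP must say which recorded attributes count and what date is used.

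If the sponsor does intend a timing-only rule, SAP Section 4 should declare and justify it.

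The cost is one or two sentences in the SAP and one derivation rule. No new data are needed if occurrences already carry their own start date and intensity. If they do not, the SAP should say so and name the date to be used instead. A blinded listing of AEs that started before first dose and were ongoing at first dose would help show whether any patient is affected.

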#### Adverse events of special interest (AESIs)

A hepatic injury is defined by the following alterations of hepatic laboratory parameters:

- an elevation of AST and / or ALT  $\ge$  3 fold ULN combined with an elevation of total bilirubin  $\ge$  2 fold ULN measured in the same blood draw sample; and / or
- marked peak aminotransferase (ALT and / or AST) elevations  $\geq 10$  fold ULN.

See CTP Section 5.3.6.1.

#### Other significant AE (according to ICH E3)

According to ICH E3 (9), AEs classified as "other significant" needs to be reported and will include those non-serious and non-significant AEs with

- 1. action taken = discontinuation' or 'action taken = reduced'; or
- 2. marked haematological and other lab abnormalities or lead to significant concomitant therapy as identified by the Clinical Monitor / Investigator during medical quality review at TOM.

An overall summary of AEs will be presented.

The frequency of subjects with AEs will be summarised by treatment, primary system organ class (SOC) and preferred term (PT). The SOCs will be sorted by default alphabetically and PTs will be sorted by frequency within an SOC. Separate tables will be provided for patients with

- related AEs
- serious AEs
- serious related AEs
- AESIs
- Other significant AE (according to ICH E3)
- AEs leading to death
- AE leading to discontinuation of trial medication
- AEs occurred with incidence in the preferred term >2%
- AEs occurred with incidence in the preferred term >5%
- AEs occurred during the follow-up period.

#### 7.8.2 Laboratory data

The analyses of laboratory data will be descriptive in nature and will follow (10).

Descriptive statistics for laboratory values will be displayed using the converted values. Shift tables of change in laboratory measurements between baseline and worst value on treatment, between baseline and last value on treatment, and between worst and last value on treatment will also be presented.

